## BACKGROUND AND SIGNIFICANCE

Hyperthyroidism is a state of overactive thyroid gland due to autoimmune Graves' Disease, toxic multinodular goitre or toxic adenoma. Radioactive iodine (RAI) therapy is a common treatment modality for hyperthyroidism either as primary treatment or after failure of medical treatment. The aim of radioactive iodine therapy is a stable restoration to euthyroid state, however, a substantial proportion of patients become hypothyroid.

Although generally safe, radioiodine therapy has some potential side effects include gastrointestinal symptoms, radiation thyroiditis, sialadenitis/xerostomia, bone marrow suppression, gonadal damage and pulmonary fibrosis. Therefore it is pivotal to render cure in patients who are undergoing radioactive iodine at the first attempt to minimize the unwanted adverse effects.

Cure rate within a year post RAI is around 72%, however cure rates seems to differ from centre to centre. Several factors have been found to affect the success of RAI therapy and some of the known ones are prior use of thionamide, hyperthyroid state, gender, dose of RAI, RAI uptake and retention of RAI in the thyroid gland.

Simultaneous use of antithyroid drug (ATD) with RAI has consistently been shown to result in lower efficacy and higher failure rate than treatment with RAI alone. Antithyroid drug have a radioprotective effect and pre-treatment with ATD has been shown to increase the risk of treatment failure with subsequent RAI. The result is consistent even if the drugs are discontinued 4-7 days before RAI therapy. Carbimazole (CMZ) is the current standard therapy in the management of hyperthyroidism prior to radioactive iodine therapy. Connell *et al.*, reported that CMZ stopped 5 days before RAI reduced the rate of hypothyroidism at 1-year compared to non-pretreated patients. There are two other studies that have reported CMZ pre-treatment reduced the efficacy of RAI therapy. In a meta-analysis of 14 randomized controlled trials, adjunctive ATD, including CMZ, was associated with an increased risk of treatment failure with RAI. Despite these evidences, ATD are still being given in clinical practice prior to RAI in an attempt to avoid thyroid storm associated with high levels of thyroid hormones prior to RAI administration.

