## **METHODOLOGY**

### Study Design

This is a prospective randomized, open label, single center interventional study comparing the effectiveness of lithium versus carbimazole in lowering the thyroid hormone levels in patients undergoing radioactive iodine.

Patients will be randomized into lithium or carbimazole arms in a 1:1 ratio. Patients will receive either lithium carbonate 300mg once daily or carbimazole 10mg once daily, which is the current standard therapy. The necessary precautions will be given with regards to the study drugs. Patients will be on the above treatment for a duration of 2 months and carbimazole will be stopped 3 days prior to radioactive iodine treatment whereas lithium will be discontinued on day 3 post RAI as per usual practice. RAI will be administered at a fixed dose of 15mCi in both groups.

Antithyroid drug (ie. Methimazole or carbimazole) is restarted if needed (in symptomatic patients with FT4 of more than 40 pmol/L) at least a week after radioactive iodine and titrated as per standard treatment protocol.

Patients are declared to be cured at the end of 6 months based on thyroid function test and requirement of treatment either with thyroxine or antithyroid drug.

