### Randomization

Block randomization method will be utilised to randomize subjects into the two groups by selecting treatment arm from a box consisting of 8 options (4 lithium and 4 carbimazole). Once the box is empty, it will replenished by the same 8 options.

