## Sample size

Sample size calculation was calculated using two population proportion formulae. Prior data indicate that the proportion of cure of the patients receiving lithium was 0.91 (Bogazzi et al.) and the proportion of cure of the patients receiving carbimazole was 0.57 (Kartamihardja et al.) Thus a minimum sample size of 34 samples per group to be able to reject null hypothesis with probability power of 0.9. The type 1 error probability associated with this test of the null hypothesis is 0.05. Person's Chi Square test for independence will be used to evaluate this null hypothesis. With additional of two 20% dropout rate, the sample size is 43 samples per group.

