### Informed Consent

Patients shall be informed of the study during their usual clinic visits. They will be requested to contact investigators if they are interested. An appointment will be made where the patient information sheet will be provided and explained to them. If they are willing to participate, the consent forms will be signed and dated. If they need to, they are allowed to take the information sheet home to consult with their family members, and another day for getting consent arranged.

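### Drawing from a box of 4 + 4 slips refilled only when empty, in an open-label single-centre trial, makes about 16 of 86 allocations (19%) knowable with certainty before enrolment

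*Protocol*

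**What the plan says.** Under Methodology, Randomization, the protocol calls the method block randomization and has each subject allocated "by selecting treatment arm from a box consisting of 8 options (4 lithium and 4 carbimazole"). It continues: "Once the box is empty, it will replenished by the same 8 options". Slips are therefore drawn without replacement, and every block has size 8.

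Under Study Design: "This is a prospective randomized, open label, single center interventional study", and "Patients will be randomized into lithium or carbimazole arms in a 1:1 ratio". The synopsis sets the total at 86 subjects, and the section on refusals and withdrawals says that withdrawn subjects are not replaced, so about 86 draws are expected.

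Two other sections bear on the point:

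- **Informed Consent.** Interested patients contact the investigators and an appointment is made. If they wish to take the information sheet home first, the section allows "another day for getting consent arranged".
- **Background and Significance.** Among the factors said to affect the success of radioactive iodine, "some of the known ones are prior use of thionamide, hyperthyroid state, gender".

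The Randomization section does not say who draws the slip, who keeps the box, or at what point after consent the draw is made.

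**The concern.** Randomization protects against selection only while the person enrolling a patient cannot tell which arm comes next. Here the block size and refill rule are public and constant, and treatment is visible at the only recruiting site. A running count of past allocations is then enough to work out some future ones exactly.

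At stake is who is enrolled next, or when. Consent appointments are arranged and can move to another day, so the order of entry is not fixed. Some factors that the protocol itself links to outcome (earlier thionamide use, hyperthyroid state, gender) could be known to a recruiter before the draw. Measured factors can be partly adjusted for in the analysis; unmeasured ones cannot. The laboratory-based definition of cure gives no protection, because this kind of selection acts before allocation.

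The fault lies in a mechanism that the protocol states. A separate statistical analysis plan would not alter how slips are drawn in the clinic.

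**Working it through.** **Inputs.** Block of 4 lithium and 4 carbimazole, refilled when empty (Randomization). Open label, one centre, 1:1 (Study Design). Total of 86 (Research Synopsis; Sample size).

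**The plan's own figure.** The protocol gives no figure for predictability; the figure it does give is the sample size. With cure proportions 0.91 and 0.57 and its own rounded inputs, {1.96√0.385 + 1.29√0.327}² / 0.34² = 33.02, rounded up to 34 per group. Then 34/0.8 = 42.5, so 43 per group and 86 in total. This is reproduced, and 86 is used below.

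**Certain draws in one box.** There are C(8,4) = 70 equally likely orders. Draw *i* is certain if all four slips of one drug are among the first *i* − 1 draws, which happens in 2 × C(*i* − 1, 4) orders.

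| Draw | Orders in which it is certain | Chance |
|---|---|---|
| 1 to 4 | 0 of 70 | 0% |
| 5 | 2 × C(4,4) = 2 | 2.9% |
| 6 | 2 × C(5,4) = 10 | 14.3% |
| 7 | 2 × C(6,4) = 30 | 42.9% |
| 8 | 2 × C(7,4) = 70 | 100% |

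Expected number per box: (2 + 10 + 30 + 70)/70 = 112/70 = 1.6. As a cross-check, full enumeration gives 1, 2, 3 or 4 certain draws in 40, 20, 8 and 2 orders: (40 + 40 + 24 + 8)/70 = 1.6.

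**Over 86 patients.** 86 = 10 full boxes + 6 draws.

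- Ten boxes: 10 × 1.6 = 16.0
- First six draws of the eleventh: (2 + 10)/70 = 0.17
- Total: 16.17; 16.17/86 = 18.8%

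Simulation gives a mean of 16.2 and a central 95% range of 12 to 22. The count cannot be below 10 if 86 enrol, because the last slip of each full box is always certain.

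**Alternatives.** Trials of 86 were simulated for each scheme. The observer knows which block sizes are in use and tracks every possible position within a block. A guess names the arm with fewer allocations so far (a coin toss when level).

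| Scheme | Certain allocations of 86 | Correct guesses | Final difference above 2 |
|---|---|---|---|
| Box of 8 | 16.2 (18.8%) | 66.1% | 0% |
| Random 6/8/10 | 1.4 (1.6%) | 66.2% | 1.2% |
| Random 4/6/8 | 2.0 (2.4%) | 67.9% | 0.3% |
| Random 4/6 | 4.8 (5.5%) | 69.1% | 0% |

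Allocations predictable with at least 75% probability: 22.8 with the box, 22.3 with 6/8/10. With at least 90%: 16.2 and 3.0.

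**Largest imbalance at 86.** With the box, ten full boxes give 40 v 40 and the last six draws add at most 4 v 2, hence 44 v 42. With 6/8/10, a cut-off block of 10 can leave a difference of 4, hence 45 v 41.

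**The case against.** The strongest reply is that counting only certain allocations flatters the remedy. A recruiter need not be certain in order to steer. Allocations predictable at 75% or better hardly change with varying blocks, and the overall guess rate stays near 66%. This stands: varying the block size removes the near-certain tail and little else. The remaining guessing has to be dealt with by independent custody and by opening the allocation only after consent.

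Second, the figure of 16.2 supposes someone who keeps an accurate ordered count and knows where each box begins. Open label makes each patient's arm visible; it does not prove that anyone keeps such a count. This also stands, and is why the claim is limited to what could be known.

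Third, the extra day for consent is there for patients who want to consult their family, and patients partly set the order by coming forward themselves. Eligibility also caps FT4 and the radioiodine activity is fixed, which narrows the room for selection on those two factors. These points weaken the route to harm without closing it: appointments are still arranged, and gender and earlier thionamide use remain open to selection.

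Fourth, the Setting section already places consent and baseline assessment before study drug. It does not say when the slip is drawn, and a recruiter who can work out the next arm knows it before consent in any case.

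Finally, fixed blocks of 8 are a recognised valid method and hold the 1:1 balance. That is true, but validity of the method does not supply concealment.

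**Conclusion.** The concern holds. As written, the allocation procedure makes an expected 16.2 of 86 allocations (18.8%; 12 to 22 in 95% of simulated trials, never fewer than 10) certain in advance to an observer who tracks past draws. The arithmetic follows exactly from the stated box and refill rule. It assumes that 86 patients are drawn in sequence and that the count is kept accurately.

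What is established is that the next arm can be known. It is not shown that anyone will know it or act on it, and no size of bias in the cure proportion is claimed, because that would need assumptions the protocol does not support. The point is worth correcting because the remedy costs almost nothing, not because damage has been demonstrated.

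**What to change.** In the Randomization section, replace the box with the following:

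1. A computer-generated 1:1 list in permuted blocks of randomly varying size, with the sizes not disclosed to the site. Avoid small blocks: 6/8/10 does better than 4/6 on both certainty and guessing.
2. Custody by an existing staff member who does not recruit, for example with sequentially numbered, sealed, opaque envelopes.
3. Each allocation opened only after consent is signed and baseline data are recorded.

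The exact sizes should sit in a restricted document, not in the protocol. Items 2 and 3 are essential, since item 1 alone leaves guessing at about 66%.

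**Gain.** Certain allocations fall from 16.2 to about 1.4 of 86, even for someone who knew the sizes in use, and the sequence can be audited afterwards.

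**Cost.** One list and 86 envelopes; no added visits or posts. The downside is a slightly larger possible final imbalance, up to 45 v 41 instead of 44 v 42, with a difference above 2 in about 1% of simulated trials.

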### Assays and values

#### *Thyroid Function Test*

Thyroid Stimulating Hormone (TSH) and Free T4 (FT4) are measured using Chemiluminescent Microparticle Immunoassay (CMIA) method.

The normal range for TSH is 0.35-4.94 uIU/ml and for FT4 is 9-19.05 pmol/L.

#### *Renal Profile*

Renal profile is measured by Indirect Ion selective electrode (ISE) method, and urea and creatinine are measured using urease and Jaffe's method respectively.

The normal range for creatinine is 50.4-98.1 umol/L.

#### *eGFR*

eGFR is calculated using MDRD formula:  $186 \times (\text{creatinine}/88.4)^{-1.154} \times (\text{age})^{-0.203} \times (0.742 \text{ if female}) \times (1.210 \text{ if black})$

#### *Lithium Therapeutic Drug monitoring*

Lithium level measured using Colorimetric method. Target serum concentration ranges from 0.6-1.2mM. Serum level >1.5mM is associated with sharp increase in severe adverse effects.

### *Definition of cure*

Cure is defined as achievement of euthyroidism or hypothyroidism at 6 months after radioactive iodine therapy. Euthyroidism is defined as having serum TSH and Free T4 level within normal range without anti thyroid drug. Hypothyroidism is defined as having elevated TSH with low or normal free T4 level or requiring thyroxine replacement.

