### Setting

Patients who are able to comply with the requirement of radioiodine therapy and consented to participate in this trial will be given appropriate counselling. These patients will be screened for inclusion and exclusion criteria. A written informed consent will be obtained and patients will then be recruited into this study.

Once recruited, history, physical examination including baseline eye examination for possible Thyroid Eye Disease (TED) will be carried out. *TED* as defined according to the presence of eye signs in categories 2–6 of the NOSPECS classification and determined clinical activity score of thyroid eye disease according to EUGOGO criteria.

Patients will be then assessed for baseline thyroid function test (TFT), renal profile (RP) and liver function test (LFT) during screening. Patients will receive either lithium carbonate 300mg once daily or carbimazole 10mg once daily, which is the current standard therapy. The necessary precautions will be given with regards to the study drugs.

Patients will be enquired of any possible side effects during the clinic visits. Lithium levels will be checked at week 1 and at the end of 2 months of initiation (refer study flow chart). If patient develops intolerable side effects or the lithium level exceeded therapeutic range, the confounding drug will be stopped and patient will be managed accordingly. The patient will subsequently be withdrawn from the study. It is important to note that the lithium dose used in this study is of low dose, hence the side effects risks anticipated would be low.

Current waiting period in PPUKM is about 2months. Patients will be on the above treatment for a duration of 2 months and carbimazole will be stopped 3 days prior to radioactive iodine treatment. RAI will be administered at a fixed dose of 15mCi in both groups. Bloods will be drawn for TFT, RP, LFT and lithium level on the RAI day. Lithium will be discontinued on day 3 post RAI. The timeline for stopping both the carbimazole and lithium are as per clinical practice guidelines. Patients will be followed up at months 1, 3 and 6 post RAI with TFT during each visit.

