## Inclusion Criteria

- Adult patients aged 18 years old and above with thyrotoxicosis who have been planned for definitive RAI:
  - consented for radioactive therapy as a definitive treatment.
  - able to comply with requirement of radioiodine therapy.
  - FT4 level below 40pmol/L

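### The off-antithyroid-drug condition applies to only one leg of the cure definition, so a patient still on the drug with raised TSH at 6 months counts as cured

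*Protocol*

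**What the plan says.** Under Definition of cure, a patient is cured if euthyroid or hypothyroid 6 months after RAI. The two legs are worded differently:

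- Euthyroid leg: "Euthyroidism is defined as having serum TSH and Free T4 level within normal range without anti thyroid drug".
- Hypothyroid leg: "Hypothyroidism is defined as having elevated TSH with low or normal free T4 level or requiring thyroxine replacement".

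The laboratory limits are under Thyroid Function Test: "The normal range for TSH is 0.35-4.94 uIU/ml and for FT4 is 9-19.05 pmol/L".

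Study Design says that antithyroid drug "is restarted if needed (in symptomatic patients with FT4 of more than 40 pmol/L) at least a week after radioactive iodine" and is then titrated under a standard treatment protocol that is not reproduced. The same section says that cure is declared at 6 months "based on thyroid function test and requirement of treatment either with thyroxine or antithyroid drug". On monitoring, Setting says: "Patients will be followed up at months 1, 3 and 6 post RAI with TFT during each visit".

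**The concern.** Drug status decides the outcome in one leg and is ignored in the other. Antithyroid drug lowers thyroid hormone and can raise TSH, so a raised TSH on the drug may reflect the drug and not the RAI. The written rule nevertheless scores that patient as an RAI cure.

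Study Design lists need for antithyroid drug as an input to the cure decision, which suggests it was meant to count against cure. It does not say so, and it lists thyroxine need, which does count as cure, in the same phrase.

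At stake is the primary endpoint of an open-label trial. Where the text supports two readings, the person declaring cure may know the arm when choosing between them. If true failures are scored as cures in both arms, the difference between arms shrinks and some power is lost.

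**Working it through.** **1. Apply the written rule.** Take a patient taking antithyroid drug, and not thyroxine, at the month 6 visit:

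| Month 6 result on the drug | Euthyroid leg | Hypothyroid leg | Scored |
|---|---|---|---|
| TSH 0.35–4.94, FT4 9–19.05 | fails (on drug) | fails (TSH not raised) | not cured |
| TSH above 4.94, FT4 19.05 or lower | fails | met | cured |

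Drug status is the same in both rows, and TSH passing 4.94 reverses the result.

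**2. Who can be in the second row.** Restart needs symptoms and FT4 above 40 pmol/L, which is above the entry ceiling ("FT4 level below 40pmol/L"). The patient must also still be on the drug at month 6 and have raised TSH despite titration. No thyroid test is scheduled between months 3 and 6, although routine care may add one. The protocol gives no rate for any of these steps.

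**3. Reproduce the plan's figure.** Inputs from Sample size: cure rates 0.91 (lithium) and 0.57 (carbimazole), two-sided alpha 0.05, power 0.90. The printed formula with its own rounded terms is (1.96√0.385 + 1.29√0.327)² / 0.34² = 33.02, rounded up to 34. Unrounded terms give 32.85, so 33. With 20% dropout, 34/0.80 = 42.5, so 43 per arm. The stated size reproduces to within rounding.

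**4. Effect of the literal rule (assumed shares).** Take 0.91 and 0.57 as the true off-drug cure rates and let a share f of true failures in each arm be scored as cured. The scored rate is p + f(1 − p), and the difference is 0.34(1 − f). Power is exact: the two binomials are summed over all tables with uncorrected Pearson chi-square above 3.841.

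| f | Scored rates | Difference (points) | Power, 34/arm | Power, 43/arm | False cures at 43/arm (carbimazole; lithium) |
|---|---|---|---|---|---|
| 0 | 0.910 vs 0.570 | 34.0 | 0.928 | 0.970 | 0; 0 |
| 2% | 0.9118 vs 0.5786 | 33.3 | 0.921 | 0.966 | 0.37; 0.08 |
| 5% | 0.9145 vs 0.5915 | 32.3 | 0.910 | 0.960 | 0.92; 0.19 |
| 10% | 0.919 vs 0.613 | 30.6 | 0.888 | 0.947 | 1.85; 0.39 |

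Exact power reaches 0.90 at f = 7.4% with 34 per arm, where 34 × 0.0741 × 0.43 = 1.08 carbimazole patients are affected. With 43 per arm it does so at f = 22.7%, where 43 × 0.227 × 0.43 = 4.20 are. The normal approximation is less generous: at 34 per arm it gives 0.910, 0.888 and 0.863 for f = 0, 5% and 10%, so it crosses 0.90 before 5%.

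**5. One arm only, f = 10%.** Carbimazole only: 0.57 + 0.10 × 0.43 = 0.613, difference 0.91 − 0.613 = 29.7 points (−4.3). Lithium only: 0.91 + 0.10 × 0.09 = 0.919, difference 0.919 − 0.57 = 34.9 points (+0.9).

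**The case against.** The strongest reply is that the two sections should be read together. Thyroxine need is already a route to cure, so the natural reason for Study Design to name antithyroid-drug need is that it counts against cure. On that reading this is a drafting gap and not a rule that cures on-drug patients. The likely intent is fair, but Study Design gives no direction and does not amend the formal definition. The gap is narrowed, not closed.

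Second, the group needs four conditions together and every rate is assumed. At 5% of failures, about one patient in 86 is affected (0.92 + 0.19 = 1.11). The standard treatment protocol may also cover stopping the drug and interim tests. All of this stands and limits the weight of the point.

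Third, a patient with raised TSH on the drug may be over-treated or truly hypothyroid from RAI, so calling all of them failures is an assumption. This also stands: the protocol does not show which error is larger.

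Fourth, the reversal is triggered by a laboratory value, so open-label assessment adds little under a literal reading. That is true of the literal rule. Discretion enters only because Study Design invites a second reading.

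Finally, counts by arm and sensitivity analyses usually belong in an SAP. Their absence from the protocol is no defect, and they are offered only as part of the remedy.

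**Conclusion.** The point holds and is minor. As written, the primary endpoint scores a patient on antithyroid drug with raised TSH and low or normal FT4 as cured, and the same patient with normal tests as not cured. Study Design hints at a different rule without stating it.

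No figure in the protocol is wrong because of this. The planning target ("Thus a minimum sample size of 34 samples per group to be able to reject null hypothesis with probability power of 0.9") is put at risk only if the affected share of failures exceeds about 7% by exact power with 34 evaluable per arm, or about 23% with 43. The threshold at 34 per arm is lower on the normal approximation. These sizes rest on assumed shares and on the protocol's planning rates being the true off-drug rates. Equal shares in both arms bias toward no difference. Only an excess confined to lithium would favour lithium, by 0.9 points at 10%, and nothing in the protocol suggests one. The reading of the wording is certain; the effect on results is unknown and probably small.

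**What to change.** In Definition of cure, apply the condition to the whole definition: cure = not on antithyroid drug at the 6-month visit AND either euthyroid or hypothyroid. Have the cure sentence in Study Design refer to that definition. Report by arm how many patients are on antithyroid drug with raised TSH at month 6, and add one sensitivity analysis that scores them as cured. This changes outcome scoring only and leaves treatment as it is.

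The cost is one sentence, one cross-reference and one extra analysis. The downside is that a patient with true RAI-induced hypothyroidism who is still on the drug at month 6 would be scored not cured. If a share g of true cures in each arm were lost this way (an assumption), the scored rate would be p(1 − g):

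| g | Scored rates | Difference (points) | Power, 34/arm | Power, 43/arm | Cures lost at 43/arm (lithium; carbimazole) |
|---|---|---|---|---|---|
| 1% | 0.9009 vs 0.5643 | 33.7 | 0.916 | 0.963 | 0.39; 0.25 |
| 2% | 0.8918 vs 0.5586 | 33.3 | 0.904 | 0.955 | 0.78; 0.49 |
| 5% | 0.8645 vs 0.5415 | 32.3 | 0.864 | 0.928 | 1.96; 1.23 |

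Because either error could be the larger, the sensitivity analysis belongs with the wording change.

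### The laboratory criteria for cure omit low FT4 with TSH not raised, so for these patients the primary endpoint rests on an unblinded judgement about thyroxine

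*Protocol*

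**What the plan says.** The primary objective is the proportion cured at 6 months after radioactive iodine (RAI). Under Definition of cure, the Protocol says: "Cure is defined as achievement of euthyroidism or hypothyroidism at 6 months after radioactive iodine therapy". The first of these two states is fixed by laboratory values and by being off one class of drug: "Euthyroidism is defined as having serum TSH and Free T4 level within normal range without anti thyroid drug". The second state can be reached in two ways, by laboratory values or by a need for treatment: "Hypothyroidism is defined as having elevated TSH with low or normal free T4 level or requiring thyroxine replacement".

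The limits are under Thyroid Function Test: "The normal range for TSH is 0.35-4.94 uIU/ml and for FT4 is 9-19.05 pmol/L".

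Study Design adds how the decision is reached: "Patients are declared to be cured at the end of 6 months based on thyroid function test and requirement of treatment either with thyroxine or". The sentence closes by naming the drugs used against hyperthyroidism as the other treatment considered. The same section describes the trial as open label and allows antithyroid drug to be restarted after RAI. On timing, Setting says: "Patients will be followed up at months 1, 3 and 6 post RAI with TFT during each visit".

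**The concern.** The definition intends hypothyroidism after RAI to count as success, but its laboratory wording recognises hypothyroidism only when TSH is raised. FT4 below range with TSH low or normal falls outside both laboratory descriptions. If no one judges that thyroxine is needed, a patient whose thyroid hormone is below normal off all drugs gets the same score as one who is still hyperthyroid.

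Two patients with identical month-6 results can also be scored differently, depending on whether the treating clinician says that thyroxine is needed. The Protocol ties that judgement to no laboratory value, and the clinician knows the arm. For these patients the primary endpoint is not fixed by the measurements collected for it.

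**Working it through.** **Inputs.** TSH range 0.35-4.94 uIU/ml and FT4 range 9-19.05 pmol/L (Thyroid Function Test); the cure limbs (Definition of cure); 34 per group before and 43 after dropout, with planned cure rates 0.91 and 0.57 (Sample size).

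**Step 1. Apply the rule to every pattern.** For a patient on neither drug and not judged to need thyroxine:

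| | FT4 < 9 | FT4 9-19.05 | FT4 > 19.05 |
|---|---|---|---|
| TSH < 0.35 | not cured | not cured | not cured |
| TSH 0.35-4.94 | not cured | cured | not cured |
| TSH > 4.94 | cured | cured | not cured |

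Of the three low-FT4 cells, one counts as cure. Two examples are FT4 7 with TSH 2.0, and FT4 7 with TSH 0.1. Both fail the euthyroid limb because FT4 is below 9, and both fail the raised-TSH limb because TSH is not above 4.94.

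**Step 2. Add the thyroxine limb.** This limb has no TSH condition, so either example becomes cured if thyroxine is judged to be required. The gap is therefore low FT4, TSH not raised and no such judgement at month 6.

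**Step 3. Add antithyroid drug.** The off-drug condition is written only into the euthyroid limb. As worded, raised TSH with low or normal FT4 in a patient on restarted antithyroid drug satisfies the hypothyroid limb. Any repair has to carry the off-drug condition.

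**Step 4. Size per patient.** 1/43 = 0.023, or 2.3 points; 1/34 = 0.029, or 2.9 points.

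**Step 5. The plan's own sample size.** With its rounded terms, (1.96 × √0.385 + 1.29 × √0.327)² / 0.34² = 33.02, which rounds up to 34. With unrounded terms it is 32.85. For dropout, 34 / 0.8 = 42.5, so 43. The stated figures reproduce and do not depend on the wording of the definition.

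**Step 6. Sensitivity (assumed shares; the documents give none).** Let f1 (lithium) and f2 (carbimazole) be the shares of true cures scored not cured. Then p1 = 0.91(1 − f1) and p2 = 0.57(1 − f2). With p̄ = (p1 + p2)/2 and n = 34:

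power = Φ{ [ |p1 − p2|√n − 1.96√(2p̄(1 − p̄)) ] / √(p1(1 − p1) + p2(1 − p2)) }

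| f1 (lithium) | f2 (carbimazole) | p1 | p2 | Difference | Power |
|---|---|---|---|---|---|
| 0 | 0 | 0.910 | 0.570 | 0.340 | 0.91 |
| 0.02 | 0.02 | 0.892 | 0.559 | 0.333 | 0.89 |
| 0.05 | 0.05 | 0.864 | 0.541 | 0.323 | 0.85 |
| 0.10 | 0.10 | 0.819 | 0.513 | 0.306 | 0.78 |
| 0.05 | 0 | 0.864 | 0.570 | 0.294 | 0.78 |
| 0.10 | 0 | 0.819 | 0.570 | 0.249 | 0.61 |
| 0 | 0.05 | 0.910 | 0.541 | 0.369 | 0.94 |

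The result runs from little effect to a large one, and the sign depends on which arm is affected.

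**The case against.** The strongest reply is that the definition does have a route for these patients. The thyroxine limb carries no TSH condition. It speaks of needing thyroxine rather than already taking it, so it can be judged at the month-6 visit itself, and Study Design makes that need part of the decision. This stands. A reader might infer that the definition has no place at all for low FT4 with TSH not raised, and the text does not support that. What remains is the patient who is not judged to need thyroxine, and the fact that this judgement has no criterion and is not blinded.

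A second reply is that nothing in the documents shows the pattern to be common. That also stands. Background and Significance says that many patients become hypothyroid after RAI. It does not say how many have low FT4 without raised TSH at 6 months.

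A reader might also infer a bias against lithium, since the Protocol describes antithyroid drug as radioprotective and lithium as increasing RAI retention. The documents do not establish this. The hypothesis is more cure with lithium, not more of this particular pattern. Earlier ablation would also leave more time for TSH to rise or for thyroxine to be judged necessary before month 6, which could make the loss smaller in that arm.

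Finally, treatment failure is not a category in the Protocol. Scoring these patients as not cured follows from comparing a proportion cured.

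**Conclusion.** The point holds in limited form. Both laboratory limbs miss FT4 below 9 pmol/L with TSH not above 4.94 uIU/ml. Off antithyroid drug, such a patient is cured or not cured according to an open-label judgement with no stated criterion. If thyroxine is not judged necessary, the score contradicts the definition's own aim of counting hypothyroidism as cure.

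The size per patient is 2.3 points of an arm's cure rate with 43 analysed, or 2.9 points with 34. The total effect and its direction are unknown. The power figures above rest on assumed shares and on the planned rates of 0.91 and 0.57, and show only the range. They do not mean that the sample size was miscalculated or that the comparison is known to be biased towards no difference. The case for correction is that a primary endpoint should follow from the measurements already taken, and here it does so with one sentence.

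**What to change.** Under Definition of cure, replace the hypothyroidism sentence with an endpoint definition such as this. In a patient off antithyroid drug, hypothyroidism is any of:

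- FT4 below 9 pmol/L whatever the TSH;
- TSH above 4.94 uIU/ml with FT4 low or normal;
- a requirement for thyroxine.

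The off-drug condition must govern all three limbs. Without it, low FT4 on restarted antithyroid drug would count as cure, as raised TSH on that drug does under the present wording.

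In the same place, state how low TSH with normal FT4 off antithyroid drug is scored. It also fits neither laboratory limb and is now not cured by default.

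The change affects outcome classification only and sets no rule for giving or withholding any drug. It needs no new tests or visits, because TSH and FT4 are already measured at month 6. The cost is one or two sentences in an amendment. It should be made before outcomes are classified, because a later ruling on individual patients would be made with the arm known. If some outcomes have already been classified, derive all of them again from the recorded values and report the result under both definitions.
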